### Hospitalization

Hospitalization is defined as any initial admission (even if less than 24 hours) to a hospital or equivalent healthcare facility or any prolongation to an existing admission. Admission also includes transfer within the hospital to an acute/intensive care unit (e.g., from the psychiatric wing to a medical floor, medical floor to a coronary care unit, neurological floor to a tuberculosis unit). An emergency room visit does not necessarily constitute a hospitalization; however, an event leading to an emergency room visit should be assessed for medical importance.

Hospitalization in the absence of a medical AE is not in itself an AE and is not reportable. For example, the following reports of hospitalization without a medical AE are not to be reported.

- Social admission (e.g., patient has no place to sleep)
- Administrative admission (e.g., for yearly exam)
- Optional admission not associated with a precipitating medical AE (e.g., for elective cosmetic surgery)
- Hospitalization for observation without a medical AE
- Admission for treatment of a pre-existing condition not associated with the development of a new AE or with a worsening of the pre-existing condition (e.g., for work-up of persistent pre-treatment lab abnormality)
- Protocol-specified admission during clinical study (e.g., for a procedure required by the study protocol)

### **5.2.3. Scenarios necessitating reporting to Pfizer Safety within 24 hours**

Scenarios involving exposure during pregnancy, exposure during breastfeeding, medication error, overdose, misuse, extravasation, lack of efficacy, and occupational exposure are described below.

#### Exposure during pregnancy

An exposure during pregnancy (EDP) occurs if:

1. A female becomes, or is found to be, pregnant either while receiving or having been exposed to (e.g., environmental) Inlyta, or the female becomes, or is found to be, pregnant after discontinuing and/or being exposed to Inlyta (maternal exposure).

An example of environmental exposure would be a case involving direct contact with a Pfizer product in a pregnant woman (e.g., a nurse reports that she is pregnant and has been exposed to chemotherapeutic products).

2. A male has been exposed, either due to treatment or environmental exposure to Inlyta prior to or around the time of conception and/or is exposed during the partner pregnancy (paternal exposure).

As a general rule, exposure during pregnancy reports from any source are reportable irrespective of the presence of an associated AE and the procedures for SAE reporting should be followed.

If a study participant or study participant's partner becomes, or is found to be, pregnant during the study participant's treatment with Inlyta, this information must be submitted to Pfizer, irrespective of whether an adverse event has occurred using the NIS AEM Report Form and the EDP Supplemental Form.

In addition, the information regarding environmental exposure to Inlyta in a pregnant woman (e.g., a subject reports that she is pregnant and has been exposed to a cytotoxic product by inhalation or spillage) must be submitted using the NIS AEM Report Form and the EDP supplemental form. This must be done irrespective of whether an AE has occurred.

Information submitted should include the anticipated date of delivery (see below for information related to termination of pregnancy).

Follow-up is conducted to obtain general information on the pregnancy; in addition, follow-up is conducted to obtain information on EDP outcome for all EDP reports with pregnancy outcome unknown. A pregnancy is followed until completion or until pregnancy termination (e.g., induced abortion) and Pfizer is notified of the outcome. This information is provided as a follow up to the initial EDP report. In the case of a live birth, the structural integrity of the neonate can be assessed at the time of birth. In the event of a termination, the reason(s) for termination should be specified and, if clinically possible, the structural integrity of the terminated fetus should be assessed by gross visual inspection (unless pre-procedure test findings are conclusive for a congenital anomaly and the findings are reported).

If the outcome of the pregnancy meets the criteria for an SAE (e.g., ectopic pregnancy, spontaneous abortion, intrauterine fetal demise, neonatal death, or congenital anomaly [in a live born, a terminated fetus, an intrauterine fetal demise, or a neonatal death]), the procedures for reporting SAEs should be followed.

Additional information about pregnancy outcomes that are reported as SAEs follows:

- Spontaneous abortion includes miscarriage and missed abortion;
- Neonatal deaths that occur within 1 month of birth should be reported, without regard to causality, as SAEs. In addition, infant deaths after 1 month should be reported as SAEs when the investigator assesses the infant death as related or possibly related to exposure to investigational product

Additional information regarding the exposure during pregnancy may be requested. Further follow-up of birth outcomes will be handled on a case-by-case basis (e.g., follow-up on preterm infants to identify developmental delays).

In the case of paternal exposure, the study participant will be provided with the Pregnant Partner Release of Information Form to deliver to his partner. It must be documented that the study participant was given this letter to provide to his partner.

#### Exposure during breastfeeding

Scenarios of exposure during breastfeeding must be reported, irrespective of the presence of an associated AE. An exposure during breastfeeding report is not created when a Pfizer drug specifically approved for use in breastfeeding women (e.g., vitamins) is administered in accord with authorized use. However, if the infant experiences an AE associated with such a drug's administration, the AE is reported together with the exposure during breastfeeding.

#### Medication error

A medication error is any unintentional error in the prescribing, dispensing or administration of a medicinal product that may cause or lead to inappropriate medication use or patient harm while in the control of the health care professional, patient, or consumer. Such events may be related to professional practice, health care products, procedures, and systems including: prescribing; order communication; product labeling, packaging, and nomenclature; compounding; dispensing; distribution; administration; education; monitoring; and use.

Medication errors include:

- Near misses, involving or not involving a patient directly (e.g., inadvertent/erroneous administration, which is the accidental use of a product outside of labeling or prescription on the part of the healthcare provider or the patient/consumer);
- Confusion with regard to invented name (e.g., trade name, brand name).

The investigator must submit the following medication errors to Pfizer, irrespective of the presence of an associated AE/SAE :

- Medication errors involving patient exposure to the product, whether or not the medication error is accompanied by an AE.
- Medication errors that do not involve a patient directly (e.g., potential medication errors or near misses). When a medication error does not involve patient exposure to the product the following minimum criteria constitute a medication error report:
  - An identifiable reporter;
  - A suspect product;
  - The event medication error.

### Overdose, Misuse, Extravasation

Reports of overdose, misuse, and extravasation associated with the use of a Pfizer product are reported to Pfizer by the investigator, irrespective of the presence of an associated AE/SAE.

### Lack of Efficacy

Reports of lack of efficacy to a Pfizer product are reported to Pfizer by the investigator, irrespective of the presence of an associated AE/SAE or the indication for use of the Pfizer product.

### Occupational Exposure

Reports of occupational exposure to a Pfizer product are reported to Pfizer by the investigator, irrespective of the presence of an associated AE/SAE.

## **5.3. COMMUNICATION OF ISSUES**

In the event of any prohibition or restriction imposed (eg, clinical hold) by an applicable Competent Authority in any area of the world, or if the physician is aware of any new information which might influence the evaluation of the benefits and risks of INLYTA®, Pfizer should be informed immediately.

In addition, the physician will inform Pfizer immediately of any urgent safety measures taken by the physician to protect the study subjects against any immediate hazard, and of any serious breaches of this NI study protocol that the physician becomes aware of.

## **5.4. SINGLE REFERENCE SAFETY DOCUMENT**

Background information on INLYTA® can be obtained from the current version of the local product document, which is the single reference safety document (SRSD) for information relating to INLYTA® in this study.

## 6. STUDY DISCLOSURE

Pfizer fulfils its commitment to publicly disclose clinical trial results through posting the results of this study on [www.clinicaltrials.gov](http://www.clinicaltrials.gov). Pfizer posts the results of all studies that it has registered on ClinicalTrials.gov regardless of the reason for registration.

The results are posted in a tabular format called Basic Results.

- For studies involving a Pfizer product, the timing of the posting depends on whether the Pfizer product is approved for marketing in any country at the time the study is completed:
- For studies involving products applicable under the US Food and Drug Administration Amendments Act of 2007 (FDAAA), ie, FDA-approved products, Pfizer posts results within one year of the primary outcome completion date (PCD). For studies involving products approved in any country, but not FDA approved, Pfizer posts results one year from last subject, last visit (LSLV).
- For studies involving products that are not yet approved in any country, Pfizer posts the results of already-completed studies within 30 days after US regulatory approval, or one year after the first ex-US regulatory approval of the product (if only submitted for approval ex-US);
- For studies involving products whose drug development is discontinued before approval, Pfizer posts the results within one year after such discontinuation of the program (if there are no plans for outlicensing or within two years if outlicensing plans have not completed).
- Primary Completion Date is defined as the date that the final subject was examined or received an intervention for the purposes of final collection of data for the primary outcome, whether the clinical trial concluded according to the pre-specified protocol or was terminated.

## 7. LIST OF FIGURES

1. <Figure 1> Data Management Flow Chart

2. <Figure 2> Data Validation Flow Chart

## APPENDIX 2. AMENDMENTS

Amendment number	Date	Country(ies)	Site(s)	Rationale for amendment	Protocol section(s) changed
1	03 May 2016	South Korea		-Sample size reduction -Safety reporting language	Section 3.2 Section 5 Appendix 1
2	03 Jan 2018	South Korea		Adverse events reporting criteria change	Section 3.5.4
3	19 Mar 2018	South Korea		Change in study design	Section 3.1 Section 3.5 Section 3.6 Section 4 Section 5
4	20 Apr 2018	South Korea		Change in study design	Section 3.1 Section 3.2. Section 3.5 Section 3.6 Section 5
5	16 May 2018	South Korea		Change in study design and minimum number of cases	Section 1 Section 3.1 Section 3.2. Section 3.5 Section 3.6 Section 3.7 Section 3.8 Section 3.10 Section 4

6	15 Jun 2018	South Korea	Change in study duration, sample size	Section 1 Section 3.1 Section 3.2 Section 3.5 Section 3.6 Section 3.7 Section 3.8 Section 3.10 Section 4 Section 5
---	-------------	-------------	---------------------------------------	---

### APPENDIX 3. MILESTONES

Milestone	Planned date
Start of data collection	Dec 2012
End of data collection	21 Aug 2018
Interim reports	21 Apr 2013 21 Oct 2013 21 Apr 2014 21 Oct 2014 21 Oct 2015 21 Oct 2016 21 Oct 2017 21 Apr 2019 21 Oct 2019 21 Apr 2020 21 Oct 2020

INLYTA® (Axitinib)  
A4061075 NON-INTERVENTIONAL STUDY PROTOCOL  
Amendment 8, 3019 Feb 2020

---

	21 Apr 2021
Study result report (initial 6years)	21 Nov 2018
Final study report (initial 6years + additional 3 years)	21 Nov 2021

## **APPENDIX 4. RECIST 1.1 TUMOR ASSESSMENT CRITERIA 1.1**

At baseline, individual tumor lesions will be categorized by the physician as either measurable or not, according to the criteria summarized below:

### **Measurable Lesions**

Lesions that can be accurately measured in at least one dimension (longest diameter in the plane of measurement is to be recorded) with a minimum size of:

10 mm for lesions other than lymph nodes and assessed by CT scan (CT scan slice thickness no greater than 5 mm).

10 mm for lesions assessed clinically by caliper measurement (lesions which cannot be accurately measured with calipers should be recorded as non-measurable).

20 mm for lesions assessed by chest X-ray.

15 mm in short axis for lymph nodes when assessed by CT scan (CT scan slice thickness recommended to be no greater than 5 mm).

### **Non-measurable Lesions**

Non-measurable lesions include small lesions (longest diameter <10 mm or pathological lymph nodes with a  $\geq 10$  but  $<15$  mm short axis) as well as truly non-measurable lesions. Truly non-measurable lesions include: leptomeningeal disease, ascites, pleural or pericardial effusion, inflammatory breast disease, lymphangitic involvement of skin or lung, abdominal masses identified by physical exam and not measurable by reproducible imaging techniques.

Nodes that have a short axis  $<10$  mm are considered non-pathological and should not be recorded or followed.

### **Special Considerations Regarding Specific Lesions**

#### **Bone lesions:**

Bone scan, PET scan or plain films are not considered adequate imaging techniques to measure bone lesions. However, these techniques can be used to confirm the presence or disappearance of bone lesions.

Lytic bone lesions or mixed lytic-blastic lesions, with identifiable soft tissue components, that can be evaluated by cross sectional imaging techniques such as CT or MRI can be considered as measurable lesions if the soft tissue component meets the definition of measurability described above.

Blastic bone lesions are non-measurable.

### **Cystic lesions:**

Lesions that meet the criteria for radiographically defined simple cysts should not be considered as malignant lesions (neither measurable nor non-measurable) since they are, by definition, simple cysts.

‘Cystic lesions’ thought to represent cystic metastases can be considered as measurable lesions, if they meet the definition of measurability described above. However, if non-cystic lesions are present in the same patient, these are preferred for selection as target lesions.

### **Lesions with prior local treatment:**

Tumor lesions situated in a previously irradiated area, or in an area subjected to other loco-regional therapy, are usually not considered measurable unless there has been demonstrated progression in the lesion.

### **Solitary lesions:**

If a measurable disease is restricted to a solitary lesion, its neoplastic nature should be confirmed by cytology/histology.

### **Recording Tumor Measurements**

All measurable lesions up to a maximum of 2 lesions per organ and up to 5 in total and representative of all involved organs should be identified as **target lesions** and measured and recorded at baseline and at the stipulated intervals during treatment. Target lesions should be selected on the basis of their size (lesions with the longest diameters) and their suitability for accurate repetitive measurements (either by imaging techniques or clinically).

The longest diameter will be recorded for each target lesion. The sum of the longest diameter of all target lesions will be calculated and recorded as the baseline sum diameter to

be used as reference to further characterize the objective tumor response of the measurable dimension of the disease during treatment.

One exception to the above described approach is related to pathological lymph nodes. Pathological lymph nodes are defined as measurable lesions and may be identified as target lesions if the criterion of a short axis of  $\geq 15$  mm by CT scan is met. Only the short axis of these nodes will contribute to the baseline sum. Nodal size is normally reported as two dimensions in the plane in which the image is obtained (for CT scan this is almost always the axial plane; for MRI the plane of acquisition may be axial, sagittal or coronal). The smaller of these measures is the short axis.

A sum of the diameters (longest for non-nodal lesions, short axis for nodal lesions) for all target lesions will be calculated and reported as the baseline sum diameters. The baseline sum diameters will be used as reference to further characterize any objective tumor regression in the measurable dimension of the disease.

All other lesions (or sites of disease) should be identified as **non-target lesions** and should also be recorded at baseline. Measurements are not required and these lesions should be followed as 'present', 'absent', or in rare cases 'unequivocal progression'. In addition, it is possible to record multiple non-target lesions involving the same organ as a single item on the case record form (eg, 'multiple enlarged pelvic lymph nodes' or 'multiple liver metastases').

### **Definition of Tumor Response**

#### **Target Lesions**

**Response in target lesions is defined as follows:**

**Complete Response (CR):** disappearance of all target lesions.

**Partial Response (PR):** **at** least a 30% decrease in the sum of diameters of target lesions, taking as reference the baseline sum diameters.

**Progressive Disease (PD):** at least a 20% increase in the sum of diameters of target lesions, taking as reference the smallest sum on study (this includes the baseline sum if that is the smallest on study). In addition to the relative increase of 20%, the sum must also

demonstrate an absolute increase of at least 5 mm. The appearance of one or more new lesions is also considered a sign of progression.

**Stable Disease (SD):** neither sufficient shrinkage to qualify for PR nor sufficient increase to qualify for PD, taking as reference the smallest sum diameters while on study.

When nodal disease is included in the sum of target lesions and the nodes decrease to 'normal' size (<10 mm), they may still have a measurement reported on scans. This measurement should be recorded even though the nodes are normal in order not to overstate progression should it be based on increase in size of the nodes. As noted earlier, this means that patients with CR may not have a total sum of 'zero' on the CRF.

### **Non-Target Lesions**

While some non-target lesions may actually be measurable, they need not be measured and instead should be assessed only qualitatively at the time points specified in the protocol.

### **Response in non-target lesions is defined as follows:**

**Complete Response (CR):** Disappearance of all non-target lesions and normalization of tumor marker level. All lymph nodes must be non-pathological in size (<10 mm short axis).

**Non-CR/Non-PD:** Persistence of one or more non-target lesion(s) and/or maintenance of tumor marker level above the normal limits.

**Progressive Disease (PD):** Unequivocal progression of existing non-target lesions. (Note: the appearance of one or more new lesions is also considered progression).

### **Cytology, histology**

These techniques can be used to differentiate between PR and CR in rare cases if required by protocol (for example, residual lesions in germ cell tumors). When effusions are known to be a potential adverse effect of treatment (eg, taxane compounds or angiogenesis inhibitors), the cytological confirmation of the neoplastic origin of any effusion that appears or worsens during treatment can be considered if the measurable tumor has met criteria for response or stable disease in order to differentiate between response or stable disease and progressive disease.

For patients having effusions or ascites, only cases having cytological proof of malignancy should be recorded on the CRF. Effusions that have not been evaluated using cytology or were found to be non-malignant should not be recorded on the CRF.

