## 1. RATIONALE AND BACKGROUND

Renal cell carcinoma (RCC) accounts for 85% of kidney cancers, and is a collection of different types of tumors that arise from the renal epithelium. Renal cell carcinoma (RCC) is diagnosed in approximately 170,000 patients worldwide annually, resulting in 82,000 deaths.

Early stage disease does not typically produce significant clinical signs or symptoms, consequently 25-30% of newly diagnosed patients present with advanced (including locally invasive or advanced) or unresectable disease. The 5-year survival rate for advanced RCC is estimated to be ≤10%.

Most RCCs are highly vascularised tumors that over-express a number of growth factors, including VEGF (Vascular endothelial growth factor), PDGF (Platelet-derived growth factor) and fibroblast growth factor (FGF). The clear cell RCC subtype represents approximately 85% of the RCC population and frequently displays allelic loss on chromosome 3p, accompanied by mutational inactivation of the von Hippel-Lindau (VHL) tumor suppressor gene. VHL-associated RCC are known for their vascularity and these tumors produce high levels of vascular endothelial growth factor (VEGF). In addition, recent studies suggest that in sporadic clear cell RCC, increased expression of VEGF is closely correlated with neovascularization, which is a prerequisite of tumor growth and metastasis.

INLYTA®, a substituted indazole derivative, is an oral, potent, and selective inhibitor that blocks signal transmission via vascular endothelial growth factor receptor (VEGFR-1, -2 and -3) which is related to vascularization of tumors and tumor proliferation.

INLYTA® was first approved as new medicine on 22 Aug 2012. As required for any new medication approved by Ministry of Food and Drug Safety (MFDS), safety and efficacy information of new medication should be provided at minimum 3000 subjects administered in the setting of routine practice during the initial 6 years after the approval. However, based on MFDS's review upon Pfizer Korea's request, additional 3 years of study period has been granted to collect safety and efficacy information of minimum of 100 subjects.

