## **3. RESEARCH METHODS**

### **3.1. Study design**

Observational, non-interventional drug and multi-center study in which subjects will be administered as part of routine practice at Korean health care centers by accredited physicians. At least 3000 subjects should be enrolled in this study based on the Article 6 of “Basic Standards for the Re-examination of New Medicines” notified by MFDS. However, with additional 3 years of study period, at least 100 subjects who are being treated with Inlyta within the approved indication will be studied for total of 9 years according to the review result by the MFDS per Pfizer’s request to adjust the number of subjects. The study can be performed in Korean health care centers where INLYTA® is prescribed for advanced renal cell carcinoma (aRCC) after failure of one prior systemic therapy which is the indication for INLYTA® and where post-marketing study is allowed by institutions.

To achieve the target sample size, the study is being conducted in prospective study design and retrospective study design.

Patients to whom INLYTA® is first administered or patients who are already on INLYTA® during the study period should be enrolled in the study. Observation should be done from treatment initiation of INLYTA® for at least 28 calendar days. There are no visits or activities mandated by this study and routine observation will be done during INLYTA® treatment.

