### 3.5.4.9. Safety

#### 3.5.4.9.1. Adverse Event

Every observed and reported adverse event, regardless of the causal relationship with the study drug, must be recorded on an adverse event section in case report forms. The query pattern of experience of adverse event to the subjects is as follow;

Patients who are prescribed with INLYTA® for the first time during the study period: “Have you had any health problem since last visit?”

Patients who are already on INLYTA® at the time of enrollment: all safety information will be collected from medical chart since the date of treatment initiation.

For adverse events repeating before and after administrating the study drug, record the date adverse event was first experienced and the date adverse event resolved. Background information on INLYTA® can be obtained from the current version of the local product document, which is the single reference safety document (SRSD) for information relating to INLYTA®.

Check either ‘yes’ or ‘no’ in adverse event section. If ‘yes’, record in detail.

- Adverse events: Record the name of adverse event. If possible, specify diagnosis, not individual symptoms. Record the name according to National Cancer Institute Common Terminology Criteria for Adverse Events (CTCAE) Version 5.0.
- Date of onset: Record the date of onset. Record approximate date if an actual date is unknown.
- Date of resolution: Record the date of resolution. Record approximate date if an actual date is unknown.
- Severity: Severity evaluation of adverse event must be done according to the NCI CTC grade.
  - The physician will use the following definitions of severity in accordance with the National Cancer Institute Common Terminology Criteria for Adverse Events (CTCAE) Version 5.0 to describe the maximum intensity of the adverse event:

Grade	Definition
Grade 1	Mild; asymptomatic or mild symptoms; clinical or diagnostic observations only; intervention not indicated.
Grade 2	Moderate; minimal, local or noninvasive intervention indicated; limiting age-appropriate instrumental ADL*.
Grade 3	Severe or medically significant but not immediately life-threatening; hospitalization or prolongation of hospitalization indicated; disabling; limiting self care ADL**.
Grade 4	Life-threatening consequences; urgent intervention indicated.
Grade 5	Death related to AE.

Activities of Daily Living (ADL)

\*Instrumental ADL refer to preparing meals, shopping for groceries or clothes, using the telephone, managing money, etc.

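### Appendix 4 keeps non-malignant or untested effusions off the CRF without limiting the rule to tumour assessment, so read literally it conflicts with the rule to record every adverse event

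*Protocol*

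**What the plan says.** The Cytology, histology part of Protocol Appendix 4 has two paragraphs. The first is about telling response or stable disease from progression. It opens: "When effusions are known to be a potential adverse effect of treatment (eg, taxane compounds or angiogenesis inhibitors", and says that cytology can then be considered for an effusion that appears or worsens on treatment. The second gives the recording rule in two sentences: "For patients having effusions or ascites, only cases having cytological proof of malignancy should be recorded on the CRF", and "Effusions that have not been evaluated using cytology or were found to be non-malignant should not be recorded on the CRF". Neither sentence names a page or section of the form.

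The AE rule is in Protocol 3.5.4.9.1: "Every observed and reported adverse event, regardless of the causal relationship with the study drug, must be recorded on an adverse event section" of the CRF. The table in 5.1.1 repeats it: all serious and all non-serious AEs go on the CRF. Only the serious ones also go to the sponsor's safety unit on a separate form, within 24 hours.

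Elsewhere in Appendix 4, the list of non-measurable lesions reads: "Truly non-measurable lesions include: leptomeningeal disease, ascites, pleural or pericardial effusion", among others. Recording Tumor Measurements then asks for all lesions that are not target lesions to be recorded at baseline. Neither place sets a cytology condition.

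**The concern.** Section 1 of the protocol describes the study drug as a "selective inhibitor that blocks signal transmission via vascular endothelial growth factor receptor", so the appendix's own example of angiogenesis inhibitors applies to it. The appendix thus names effusion as a possible effect of such drugs. In its next paragraph it keeps the effusions not shown to be malignant off the CRF.

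The objective in Section 2 is to monitor use of the drug in practice, including AEs. If a site took the sentence at its word, a benign or untested pleural, pericardial or abdominal effusion that was an AE would be missing from the AE and adverse drug reaction tables. The omission would also be selective, because effusions proven malignant would be kept.

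Cytology may well be missing for some patients, since Section 3.1 states: "There are no visits or activities mandated by this study". For patients already on the drug at enrolment, safety data are taken from the chart (3.5.4.9.1), so the written recording rules decide what is transferred.

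**Working it through.** No arithmetic applies: the plan states no effusion rate and no cytology rate. The check is a comparison of the texts.

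1. **Is there one CRF or several?** Protocol 3.7.1 requires a CRF for each subject and makes no separation between a tumour form and a safety form. A rule about the CRF without further words therefore covers the AE section as well.

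2. **Can both rules be followed?** Take an effusion that meets the AE definition in 5.2.1 and has no cytological proof of malignancy. Section 3.5.4.9.1 and the 5.1.1 table say that it goes on the CRF. The Appendix 4 sentence, read literally, says that it does not. Both cannot be obeyed.

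3. **Where would such an effusion be recorded?**

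| Effusion | Appendix 4 read as lesion recording only | Appendix 4 read literally |
|---|---|---|
| Proven malignant | CRF, as tumour | CRF, as tumour |
| Not proven malignant, serious AE | CRF AE section and separate safety form | Separate safety form only |
| Not proven malignant, non-serious AE | CRF AE section | Nowhere |
| Not proven malignant, not an AE | Not recorded | Not recorded |

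The two readings differ in the second and third rows. In the third there is no other route, because the 5.1.1 table sends no non-serious AEs on the separate form.

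4. **Does the CRF feed the tables?** SAP 6.2 classifies and summarises the AEs that are in the CRF. An effusion that is not entered there does not reach those tables.

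5. **Does the text point to a tumour page?** Protocol 3.5.4.10 lists two efficacy entries: the date of the scan and one box for overall response. It lists no lesion-level field, although Appendix 4 speaks of recording lesions and their sums. The CRF itself is not among the documents, so this should be checked against it.

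6. **Is Appendix 4 consistent with itself?** Non-measurable Lesions and Recording Tumor Measurements, taken together, have effusions and ascites recorded at baseline as non-target lesions. Cytology, histology has them recorded only with cytological proof. Whether an effusion is on the list of lesions can affect when progression is called, and so PFS and TTP.

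7. **Size.** The planned minimum is 100 subjects (Protocol 3.6). At that size, each subject whose effusion AE is left out lowers that line of the AE table by 1/100, or one percentage point. How many subjects that might be cannot be derived from the documents.

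**The case against.** The strongest reply is context. The sentence stands in a RECIST 1.1 appendix that opens with sorting tumour lesions and that 3.5.4.10 calls up for tumour assessment only. It lies between the rules on non-target response and those on new lesions. Where the appendix mentions the form elsewhere, it means tumour entries: nodal measurements and the target sum under Target Lesions, grouped non-target lesions under Recording Tumor Measurements. Nothing in it refers to the AE section or claims to override 3.5.4.9.1 or Section 5. On that reading no AE is lost. On the lesion lists, one can add that a general list and a specific condition can stand together.

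Most of this stands. A tumour-recording intent is likely, and the documents show no actual loss of safety data. What does not stand is that the text secures this reading: the sentence is unrestricted, and the efficacy section describes no lesion page to which it could be confined.

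A reader might infer more: that the protocol forbids recording these events as AEs, that it removes the effusions most likely to be drug effects, and that most effusions would be caught. The documents do not support this. The AE rules remain in force. An effusion without cytology in a patient with advanced renal cell carcinoma is of unknown origin, and the appendix speaks only of a potential adverse effect. That no activities are mandated does not tell us how often cytology is done. Nor is every effusion an AE: 5.2.1 sets criteria for abnormal test findings.

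**Conclusion.** The point holds as a conflict of wording with a possible safety consequence. Read literally, the recording rule in Appendix 4 contradicts 3.5.4.9.1 and 5.1.1. It could keep possible drug-related effusions out of the CRF-based AE tables. The exposure is mainly in non-serious events, which have no second route. Serious ones would still reach the safety unit on the separate form, even if they were absent from the CRF. If sites read the rule as lesion recording only, nothing is lost.

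The conclusion rests on the text alone, and any incidence put to it would be an assumption. The correction is worth making because AE monitoring is named in the objective and the remedy is small. The mismatch between the lesion lists and the cytology condition is a second, separate point, and it bears on progression rather than safety.

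**What to change.** Reword the two sentences in the second paragraph of Cytology, histology along these lines: *Effusions or ascites without cytological proof of malignancy are not recorded as tumour lesions for the RECIST assessment. This does not limit adverse event recording: any effusion or ascites that meets the adverse event definition in Section 5.2.1 is recorded in the adverse event section under 3.5.4.9.1 and Section 5, whatever the cytology, and the existing rules on disease progression are unchanged.*

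The reference to 5.2.1 is needed so that the change does not turn every new or worsening effusion into an AE. The last clause leaves in place the provisions in 3.5.4.9.1 and 5.2.2 that keep non-fatal progression and its signs out of serious AE reporting.

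In the same amendment, reconcile Non-measurable Lesions and Recording Tumor Measurements with the cytology condition, so that a site knows when an effusion or ascites counts as a non-target lesion.

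The cost is two sentences in Appendix 4, the matching adjustment to the lesion text, and a note in the CRF completion instructions. No new procedure is required.
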